#### **6.2.6. Study Exposure**

Study IP administration data will be presented in a listing.

Study duration will be summarized since date of the first/second/third study injection, since the date of the BD, and date from the last injection in Part A to BD.

#### **6.2.7. Major Protocol Deviations**

Major protocol deviations are a subset of protocol deviations that may significantly impact the completeness, accuracy, or reliability of the study data or that may significantly affect a subject's rights, safety, or well-being. Major protocol deviations rules will be developed and finalized before database lock.

The number and percentage of the subjects with each major protocol deviation type will be provided by participant group as defined in [Section 6.1](#) based all enrolled subjects.

Major protocol deviations will be presented in a listing.

#### **6.2.8. COVID-19 Impact**

A listing will be provided for the impact of COVID-19 on the execution of the study.

### **6.3. Safety and Reactogenicity Analysis**

Safety will be assessed by clinical review of all relevant parameters including solicited ARs, unsolicited AEs, SAEs, MAAEs, AESI, AEs leading to withdrawal from study vaccine and/or study participation, vital signs, and physical examination findings.

Reactogenicity will be assessed by clinical review of solicited ARs (local and systemic).

Confidential

### **6.3.1. Adverse Events**

Unsolicited AEs are collected for the purpose of assessing safety. All safety analyses will be based on the Safety Set.

A treatment-emergent AE (TEAE) is defined as any event occurring during the study not before exposure to study vaccine or any event already present that worsens after exposure to study vaccine. Worsening of a pre-existing condition after vaccination will be reported as a new AE.

Adverse events will also be evaluated by the investigator for the coexistence of MAAE which is defined as an AE that leads to an unscheduled visit to a healthcare practitioner.

Unsolicited AEs will be coded by PT and SOC using MedDRA and summarized by participant group and analysis stage (up to 28 days after any vaccination and throughout the study period from Day 1 (Part A)/BD-Day 1 (Part B)/Day 1 (Part A and Part B); see [Section 6.1](#) for definitions of participant group and analysis stage).

Similarly, adverse events related to organ rejection status will be reviewed by an adjudication committee as described in Section 7.6.1 of Protocol Amendment 4 to determine whether they represent an adjudicated biopsy-proven organ rejection. Events that are adjudicated as biopsy-proven organ rejection will be summarized for transplant recipients by participant group and analysis stage. Adjudication results will be listed.

All summary tables (except for the overall summary of AEs) for unsolicited AEs will be presented by SOC and PT for TEAEs with counts of subjects included. SOC will be displayed in internationally agreed order. PT will be displayed in descending order of frequency, overall, and then alphabetically within SOC. When summarizing the number and percentage of subjects with an event, subjects with multiple occurrences of the same AE or a continuing AE will be counted once. Subjects will be presented according to the highest severity (the strongest relationship) in the summaries by severity/grade (of related AEs), if subjects reported multiple events under the same SOC and/or PT.

Percentages will be based upon the number of subjects in the Safety Set within each participant group.

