Study Arm	Part A	Doses in P304 Part A	Part A Dose	Move on to Part B?	Part B	Doses in P304 Part B	Part B B-Dose	Total Doses in P304
SOT Recipient Cohorts								
Unvaccinated participants who consent to receive only 2 doses in Part A (Days 1 and 29)	Group A1	2	100 µg		NA	N/A	N/A	2
Unvaccinated participants who consent to receive 3 doses in Part A (Days 1, 29, and 85)	Group A2	3	100 µg	➡	Group B2	1	100 µg	4
Participants previously vaccinated with 2 doses of the Moderna COVID-19 vaccine under the EUA who consent to receive a third dose in Part A (Day 1)	Group A3	1	100 µg	➡	Group B3	1	100 µg	2
SOT recipients who completed primary vaccination with an mRNA or non-mRNA COVID-19 vaccine outside mRNA-1273-P304 who consent to receive 1 booster dose (in Part B)	N/A	N/A	N/A		Group B4	1	100 µg	1

Study Arm	Part A	Doses in P304 Part A	Part A Dose	Move on to Part B?	Part B	Doses in P304 Part B	Part B B-Dose	Total Doses in P304
Healthy Adult Cohort								
Healthy adults who consent to receive 2 doses in Part A (Days 1 and 29)	Group A5	2	100 µg	➡	Group B5	1	100 µg	3

[figure not shown]
Abbreviations: B-Dose = booster dose; EUA = Emergency Use Authorization; SOT = solid organ transplant,

Figure 1: Study Schema for Unvaccinated Participants Who Receive the 2-Dose Vaccination Regimen (Part A)

[figure not shown]
Abbreviations: CMI = cell-mediated immunity; IA = interim analysis; immuno = immunogenicity; NP = nasopharyngeal; SOT = solid organ transplant (recipients).

Figure 2: Study Schema for Unvaccinated Participants Who Receive the 3-Dose Vaccination Regimen (Part A)

Abbreviations: CMI = cell-mediated immunity; NP = nasopharyngeal; SOT = solid organ transplant (recipients).

**Figure 3: Study Schema for Previously Vaccinated Participants Who Receive a Single-dose Vaccination Regimen (dose 3)
(Part A)**

Abbreviations: CMI = cell-mediated immunity; NP = nasopharyngeal; SOT = solid organ transplant.

Figure 4: Booster Phase Study Pathway

[figure not shown]
[figure not shown]

Figure 5: Study Schema for Booster Dose Phase (Part B)

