#### 3.1. Primary Endpoints

The safety of 100 µg mRNA-1273 administered in 2-dose or 3-dose regimens will be evaluated by the following endpoints:

- Unsolicited AEs through 28 days after each injection
- Medically attended adverse events (MAAEs) from Day 1 and throughout the study period
- Serious adverse events (SAEs) from Day 1 and throughout the study period
- Adverse events of special interest (AESIs) from Day 1 and throughout the study period
- AEs leading to discontinuation from dosing and/or study participation (withdrawal) on Day 1 and throughout the study period
- Biopsy-proven organ rejection from Day 1 and throughout the study period

The reactogenicity of 100 µg mRNA-1273 administered in 2-dose or 3-dose regimens will be evaluated by the following endpoints:

- Solicited local and systemic ARs through 7 days after each injection (for unvaccinated participants who received 2 doses of mRNA-1273)
- Solicited local and systemic ARs through 7 days after each injection (for unvaccinated SOT recipients who received 3 doses and SOT recipients previously vaccinated outside the study who received a third booster dose)

The nAb responses to doses of 100 µg mRNA-1273 obtained 28 days after the second dose or third dose will be evaluated by the following endpoints:

- The geometric mean concentration (GMC) of serum SARS-CoV-2-specific nAb after the second dose (Day 57 for unvaccinated participants)
- The GMC of SARS-CoV-2-specific nAb 28 days after dose 3 (Day 113 for unvaccinated SOT recipients and Day 29 for previously vaccinated SOT recipients)

The safety of 100 µg BD of mRNA-1273 will be evaluated by the following endpoints:

- Unsolicited AEs through 28 days after BD injection
- MAAEs throughout the study period

- SAEs throughout the study period
- AESIs, including myocarditis/pericarditis throughout the study period
- AEs leading to discontinuation from dosing and/or study participation (withdrawal) throughout the study period
- Biopsy-proven organ rejection throughout the study period

The reactogenicity of 100 µg BD of mRNA-1273 will be evaluated by the following endpoint:

- Solicited local and systemic ARs through 7 days after BD injection

The nAb responses to 100 µg BD of mRNA-1273 obtained 28 days after the BD will be evaluated by the following endpoints:

- The GMC of serum SARS-CoV-2-specific nAb 28 days after the BD in SOT participants who received the Moderna primary series

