## 4. Study Design

### 4.1. Overall Study Design

This is a Phase 3b, open-label study to evaluate the safety, reactogenicity, and immunogenicity of mRNA-1273 SARS-CoV-2 vaccine in SOT recipients and healthy controls. Adult kidney and liver transplant recipients and healthy control participants who are at least 18 years of age will be enrolled at ~20 sites in US and non-US sites.

Approximately 240 adult participants (220 previously vaccinated or unvaccinated participants who have had a kidney or liver transplant and 20 unvaccinated healthy adults) will be enrolled. At least 50 SOT recipients who completed primary series vaccines with mRNA or non-mRNA COVID-19 vaccine under EUA outside the study will be enrolled in Part B (Group B4).

[figure not shown]
In Part A, all SOT recipients who were unvaccinated prior to enrollment will receive 2 doses of 100  $\mu$ g of mRNA-1273 (vaccine) 28 days apart (window of -3/+7 days for the second dose) (Group A1). The SOT recipients will be offered the opportunity to receive a third dose of vaccine at Day 85 (window of -3/+7 days for the third dose) (Group A2). All healthy participants will receive 2 doses of vaccine 28 days apart (window of -3/+7 days for the second dose) (Group A5). SOT recipients who were previously vaccinated with 2 doses of Moderna COVID-19 vaccine under the EUA prior to enrollment will receive dose 3 on Day 1 (Group A3). These participants will be referred to as previously vaccinated throughout this document.

Under Amendment 4, unvaccinated SOT participants who will be enrolled will be given 3 100  $\mu$ g doses in Part A then proceed to Part B to receive a 100  $\mu$ g booster dose (Group A2 to Group B2). SOT participants previously vaccinated with 2 doses of Moderna COVID-19 vaccine outside of the study who will be enrolled will receive a third 100  $\mu$ g dose in Part A then proceed to Part B to receive a 100  $\mu$ g BD (Group A3 to Group B3). SOT participants who completed primary series vaccines with mRNA or non-mRNA COVID-19 vaccine outside of the study who consent to receive 1 booster dose in Part B (Group B4). Healthy participants who will be enrolled will be given 2 100  $\mu$ g doses in Part A then proceed to Part B to receive a 100  $\mu$ g booster dose (Group A5 to Group B5).

In Part B, all eligible active participants in Part A will be offered to receive a 100  $\mu$ g BD of mRNA-1273 who are at least 4 months from the last dose.

[figure not shown]

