**For calculation regarding antibody levels/concentrations**, antibody values reported as below LLOQ will be replaced by  $0.5 \times \text{LLOQ}$ . Values that are greater than the upper limit of quantification (ULOQ) will be used as available. Values that are reported as greater than ULOQ ( $>\text{ULOQ}$ ) without actual values will be replaced by ULOQ for analysis. Missing results will not be imputed, unless otherwise specified.

**The following Analysis Stages** will be defined for use in this study:

- Up to 28 days after any vaccination:

This stage starts at the day of each vaccination and continues through the earliest date of (the day of each vaccination and 27 subsequent days, next vaccination [if applicable]). This analysis period will be used as the primary analysis period for safety analyses (including unsolicited AEs), except for solicited ARs, unless specified otherwise.

- Throughout the study period:

For subjects in Part A, this analysis period starts at the first study injection on Day 1 and continues through the earliest date of study completion (or prior to BD), discontinuation from the study, or death.

For subjects in Part B, this analysis period starts at the BD on BD-Day 1 and continues through the earliest date of study completion, discontinuation from the study, or death.

For subjects in Part A and Part B, this analysis period starts at the first study injection on Day 1 and continues through the earliest date of study completion, discontinuation from the study, or death.

**Unscheduled visits:** Unscheduled visit measurements will be included in the analysis as follows:

- In scheduled visit windows per specified visit windowing rules.
- In the derivation of baseline/last on-treatment measurements.
- In the derivation of maximum/minimum on-treatment values and maximum/minimum change from baseline values for safety analyses.
- In individual subject data listings as appropriate.

**Visit windowing rules:** The analysis visit windows for protocol-defined visits are provided in [Appendix B](#). Results in previously vaccinated participants who received a third

Confidential

injection in the study will be presented in tables, figures, and listings at study visits related to the third injection.

**Incomplete/missing data** will be handled by the following conventions:

- Imputation rules for missing prior/concomitant medications, non-study vaccinations and procedures are provided in [Appendix C](#).

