- Imputation rules for missing AE dates are provided in [Appendix C](#).
- For laboratory assessments, if the majority of results are indefinite, imputation of these values will be considered. If the laboratory results are reported as below the LLOQ (e.g., <0.1), the numeric values will be imputed by  $0.5 \times \text{LLOQ}$  in the summary. If the laboratory results are reported as greater than the ULOQ (e.g., >3000), the numeric values will be imputed by ULOQ in the summary.
- For immunogenicity assessments, imputation of missing results will be considered based on description in [Section 6.4](#).
- Other incomplete/missing data will not be imputed, unless specified otherwise.

**Participant groups** will be summarized according to the schema below.

- Transplant status:
  - SOT Kidney
  - SOT Liver
  - SOT Total
  - 2-Dose Healthy
- Dosing regimens:
  - Overall
  - Unvaccinated SOTs Who Received 2 Doses
  - Unvaccinated SOTs Who Received 3 Doses
  - Previously Vaccinated SOTs Who Received a Third Dose
  - Total SOTs Who Received 3 Doses
  - Primary Series All SOTs Who Received a Booster Dose
- Primary Series All SOTs Who Received a Booster Dose:
  - Overall
  - 3-Dose Moderna
  - 3-Dose Pfizer

Confidential

- Other

Unless otherwise mentioned, the results of the analyses will be summarized according to the participant groups above. Subjects under the same dosing regimen may be combined for analyses regardless of BD. Participants that received booster may be analyzed separately from participants that did not receive booster.

**Subgroup analyses** for safety and immunogenicity endpoints may be analyzed in select subgroups specified below as applicable:

- Age (18 to < 65,  $\geq$  65)
- Time of post-transplantation (< 2,  $\geq$  2 years)
- Baseline SARS-CoV-2 Status in each part (Positive, Negative) (for safety data)
- Sex (Male, Female)
- Race (White, Communities of color)
- Anti-metabolite immunosuppression (Yes, No)
- Combination of immunosuppressants (Mycophenolate, Tacrolimus, and Prednisone; Mycophenolate and Tacrolimus; Tacrolimus; and Other)
- Previous induction therapy (Basiliximab or other monoclonal antibody; Basiliximab or other monoclonal antibody with steroids; Thymoglobulin; Thymoglobulin with steroids; or steroids alone)

All analyses will be conducted using SAS Version 9.4 or higher.

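### Unsolicited AEs are not tabulated by injection, so Group A2's third-dose events appear only in listings and the combined three-dose group mixes 84 days of observation with 28

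*SAP*

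**What the plan says.** SAP Section 3.1 lists "Unsolicited AEs through 28 days after each injection" as the first of six Part A safety endpoints, alongside primary endpoints for reactogenicity and neutralizing antibody.

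SAP Section 6.1 builds one 28-day stage from the windows after all the doses. Its definition begins "This stage starts at the day of each vaccination and continues through the earliest date of", and the candidate dates are the end of the 28 days (injection day plus 27 more) and the next vaccination. On its status: "This analysis period will be used as the primary analysis period for safety analyses (including unsolicited AEs), except for solicited ARs".

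SAP Section 6.3.1 then says that unsolicited AEs will be "summarized by participant group and analysis stage (up to 28 days after any vaccination and throughout the study period". A participant with repeats of the same AE counts once, and percentages use the Safety Set of the participant group as denominator. The overall summary and the tables by system organ class, preferred term and severity (Sections 6.3.1.1 to 6.3.1.4) add no split by injection. Listings of individual unsolicited AEs are planned.

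Solicited reactions are handled differently. Section 5.4 defines a separate analysis set for the first, second, third and booster injections, and Section 6.3.2 reports each injection on its own set.

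Two groups receive a third dose in Part A. Protocol Section 3.1 (Table 2) describes Group A2 as "Unvaccinated participants who consent to receive 3 doses in Part A (Days 1, 29, and 85"). Under SAP Section 4.1, recipients previously given two doses of the same vaccine "will receive dose 3 on Day 1 (Group A3"). Section 6.1 gives each its own reporting group and adds a combined one, "Total SOTs Who Received 3 Doses".

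**The concern.** The endpoint is worded per injection, but its primary summary is per person over all injections received. Once the windows are merged, a repeated event is counted once and the denominator is the whole group, the tables hold no information on which dose an event followed.

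Two things are lost. First, A2 is the only Part A group given three study doses, so it alone could show whether unsolicited AEs change from dose 1 to dose 3, and no planned table shows that. The protocol treats the third dose as a safety question in its own right: the internal safety team reviews and the pause rules in Protocol Section 7.6.2 are tied to it. Second, the combined three-dose group adds people observed over three windows to people observed over one. Its percentage is not the risk after any particular dose, and it shifts with the numbers enrolled in A2 and A3 even if the risk after dose 3 is the same in both.

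**Working it through.** The plan gives no figure on this point. Its only safety calculation is the chance of seeing at least one rejection among 200 recipients at a true rate of 3%. That reproduces: 1 − 0.97^200 = 0.998, consistent with the stated figure of above 95%. It has no bearing on the AE tables.

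**Days at risk in the 28-day stage, Part A injections only**

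- A2: doses on Days 1, 29 and 85, so 3 × 28 = 84 days. If dose 2 is given at the early edge of its window (Day 26), the first window is cut to 25 or 26 days, depending on whether the day of the next dose is counted, and the total is 81 or 82.
- A1 and A5: two doses, 2 × 28 = 56 days.
- A3: one dose, 28 days.

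A2 is therefore observed for three times as long as A3.

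**Effect on the percentage with at least one AE**

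Inputs not in the documents, and so assumed: a risk p per 28-day window that is the same after every dose and in both groups; the within-person dependence between windows; and A2's share w of the combined group.

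A3 shows p. A2 shows p if the same people have events in every window (full dependence), and 1 − (1 − p)³ if windows are independent. I take these as the lower and upper cases.

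| Assumed p | A3 | A2, full dependence | A2, independent windows | Ratio A2:A3, upper case |
|---|---|---|---|---|
| 1% | 1% | 1% | 2.97% | 2.97 |
| 5% | 5% | 5% | 14.3% | 2.85 |
| 10% | 10% | 10% | 27.1% | 2.71 |
| 20% | 20% | 20% | 48.8% | 2.44 |
| 30% | 30% | 30% | 65.7% | 2.19 |

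**Combined three-dose group at p = 10%**

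The upper case is w × 27.1% + (1 − w) × 10%:

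- w = 25%: 0.25 × 27.1 + 0.75 × 10 = 14.3%
- w = 50%: 0.50 × 27.1 + 0.50 × 10 = 18.6%
- w = 75%: 0.75 × 27.1 + 0.25 × 10 = 22.8%

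The lower case is 10% for every w. Under the proposed by-dose table, the A2 dose-3 row, the A3 row and the combined row would each cover one 28-day window, and each would estimate p.

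**The case against.** A reader might infer that third-dose safety cannot be read from this study at all. The documents do not support that. A3 has its own reporting group and its only Part A injection is dose 3, so its 28-day row is a third-dose rate. Third-dose solicited reactions have their own set and tables, laboratory results are summarized by visit with windows around dose 3, and A2's events can be recovered from the listings.

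A reader might also infer that the SAP contradicts its endpoint. That goes too far as well. Protocol Section 7.1 uses the 28 days following each injection to describe what is collected. Protocol Section 8.3.2 asks for solicited reactions after each dose but attaches no such phrase to unsolicited AEs. The Part A objective concerns two-dose and three-dose regimens, and incidence over a whole regimen is a fair answer to it. The shortfall is one of reporting. Even so, Section 3.1 words the solicited and unsolicited endpoints alike with respect to each injection, only the solicited one is carried out by dose, and Section 8.3.2 leaves further detail to the SAP.

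A third inference is that the tables will make A2 look worse than A3. SAP Section 4.2 plans no between-group comparisons, the two groups are labelled by regimen, and the excess could be nil. This weakens the comparison between rows. It does not repair the combined estimate or supply the missing A2 rates by dose.

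Finally, the SAP already has part of the remedy. Section 6.1 presents A3 results at visits related to the third injection, and Appendix B (Table 4) aligns A3's Day 1 with A2's dose 3 for some summaries. Neither is explicitly applied to the unsolicited AE tables.

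**Conclusion.** The point holds as a reporting gap in one of several primary safety endpoints. Unsolicited AEs are tabulated in a merged 28-day stage and over the whole study, and neither separates doses. A2's third-dose events are left to listings, and the combined three-dose group mixes 84 nominal days with 28.

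The structural part follows from the text and needs no assumption. The size does. With equal risk in every window, A2's percentage lies between 1.0 and about 3 times A3's, and where it falls depends on a within-person dependence that the documents do not give. The combined percentage depends on an A2:A3 mix that they do not give either. The 27.1% for A2 and the 14.3% to 22.8% for the combined group are upper-end values at an assumed 10% risk and should not be read as predictions.

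**What to change.** In SAP Sections 6.1 and 6.3.1, add an analysis stage for the 28 days after each of dose 1, dose 2, dose 3 and the booster. Assign each AE to the most recent injection, using the study day relative to that injection already defined in Section 6.1, and use the participants who received that injection as the denominator. For the combined three-dose group, show only the dose-3 window, with A3's Day 1 aligned to A2's dose 3 as in Appendix B. Keep the merged any-vaccination summary, but by separate regimen group.

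The cost is some SAP wording and one extra set of tables. No new data are needed, and the endpoint does not change.

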#### **6.3.1.2.TEAEs by System Organ Class and Preferred Term**

The following summary tables of TEAEs will be provided by SOC and PT using frequency counts and percentages (i.e., number and percentage of subjects with an event):

- All unsolicited TEAEs
- All unsolicited TEAEs by the subgroups named in [Section 6.1](#)
- All unsolicited TEAEs that are treatment-related
- All serious TEAEs
- All serious TEAEs that are treatment-related
- All unsolicited TEAEs leading to discontinuation from study vaccine
- All unsolicited TEAEs leading to discontinuation from participation in the study

Confidential

- All unsolicited Severe TEAEs
- All unsolicited Severe TEAEs that are treatment-related
- All unsolicited medically-attended TEAEs
- All unsolicited medically-attended TEAEs that are treatment-related
- All TEAEs adjudicated as biopsy-proven organ rejection
- All TEAEs that are AESI

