### 6.5.2. Analysis of Infection Rates

For Part A and Part B, the number and percentage of subjects experiencing each of the infection events below will be summarized by participant group for the mITT Set:

- SARS-CoV-2 infection
- Asymptomatic SARS-CoV-2
- COVID-19
- Severe COVID-19
- Secondary case definition of COVID-19

For each of these summaries, the incidence rate (i.e. the infection rate) will be provided by participant group, calculated as the number of cases divided by the total person-time. The 95% CI of the incidence rate will be calculated using the exact method (Poisson distribution) and adjusted by person-time.

Person-time is defined as the total time from first dose of each part of the study (Part A or Part B) to the earliest of the following dates: date of event, dose date in next part, last date of study participation, censoring time, or efficacy data cutoff date.

For participants who are a case for symptomatic COVID-19, symptoms reported by these participants will be summarized.

For SARS-CoV-2 infection, asymptomatic SARS-CoV-2 infection, COVID-19, and severe COVID-19, the timeframe for the counting cases will begin at 14 days after the last planned dose and will differ by study arm:

- 2-dose unvaccinated without booster: from day 43 up to and including day 394,
- 3-dose unvaccinated without booster: from day 99 up to and including day 450,
- 3-dose previously vaccinated with Moderna COVID-19 vaccine without booster: from day 15 up to and including day 365.
- 2-dose unvaccinated with booster: from BD-Day 1 + 14 up to and including BD-Day 181.

Confidential

- 3-dose unvaccinated with booster: from BD-Day 1 + 14 up to and including BD-Day 181)
- 3-dose previously vaccinated with Moderna COVID-19 vaccine with booster: from BD-Day 1+ 14 up to and including BD-Day 181 .
- 3-dose previously vaccinated with mRNA or non-mRNA COVID-19 vaccine with booster: from BD-Day 1 + 14 up to and including BD-Day 181.

In addition, the COVID-19 and SARS-CoV-2 infection endpoints may be also analyzed by specimen types (i.e. NP swab, nasal swab, or saliva samples), calendar months, time periods, and all types of the diagnostic test (i.e., both RT-PCR results and other COVID-19 test results). The number and percentage of subjects experiencing COVID-19 may be summarized by specific variant groups. Listings of serum nAb and bAb levels against SARS-CoV-2, solicited ARs and unsolicited AEs will be provided for subjects infected by SARS-CoV-2.

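### In the Part A whole-study stage, follow-up stops at the booster, but rejection, SAEs, MAAEs and AESIs are reported only as crude percentages, so the Part A figure moves with booster uptake

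*SAP*

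**What the plan says.** **Measure.** SAP 6.3.1 sets the denominator: "Percentages will be based upon the number of subjects in the Safety Set within each" participant group. SAP 6.3.1.2 tabulates the serious, medically attended, AESI and rejection events as "frequency counts and percentages (i.e., number and percentage of subjects with an event". For rejection, SAP 6.3.1 adds: "Events that are adjudicated as biopsy-proven organ rejection will be summarized for transplant recipients by participant group and analysis stage". Protocol Table 6 adds event counts. Neither document plans an exposure-adjusted rate or a time-to-event summary for these endpoints.

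**Stages.** SAP 6.1 defines a 28-day stage after each vaccination and says of it: "This analysis period will be used as the primary analysis period for safety analyses (including unsolicited AEs), except for solicited ARs". It also defines whole-study stages for Part A, for Part B, and for Parts A and B together. The Part A version "continues through the earliest date of study completion (or prior to BD), discontinuation from the study, or death". The combined version starts at the first study injection and has no stop at the booster.

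**Groups.** The Part A dosing groups in SAP 6.1 (2-dose, 3-dose, previously vaccinated, total 3-dose) are not divided by booster status. The SAP says: "Subjects under the same dosing regimen may be combined for analyses regardless of BD". The next sentence reads: "Participants that received booster may be analyzed separately from participants that did not receive booster".

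**Person-time elsewhere.** SAP 6.5.2 gives infection endpoints as cases over person-time with exact Poisson intervals: "Person-time is defined as the total time from first dose of each part of the study", ending among other dates at the dose in the next part. Safety endpoints have no equivalent.

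**The concern.** Biopsy-proven rejection, SAEs, MAAEs and AESIs are primary safety endpoints assessed from Day 1 over the whole study (SAP 3.1). In the Part A whole-study stage, a participant who takes the booster leaves early, while one who declines stays for 12 months after the last dose. Both count as one person in the denominator.

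A crude percentage over unequal follow-up has no defined time horizon. The higher the booster uptake, the shorter the average follow-up and the lower the percentage, even if the underlying risk is unchanged. For rejection in transplant recipients, that shift is in the reassuring direction.

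Uptake is unlikely to be all or nothing. Protocol 3.1 offers the booster to participants already in Part A, whereas transplant recipients enrolled under Amendment 4 are to proceed to it.

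**Working it through.** **1. The plan's own figure.** SAP 4.2 and Protocol 8.1 take 200 transplant recipients and a true rejection rate of 3%, and state a probability above 95% of seeing at least one case. Check: 1 − 0.97^200 = 0.998, which agrees. The 3% carries no time frame, so it cannot be tied to any one stage.

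**2. Planned exposure in the Part A stage.** Booster days come from Protocol Table 10 (Day 120 for A3, Day 205 for A2). End days without a booster come from Protocol 3.1.1.2 (Day 365 for A3, Day 450 for A2). Exposure = (last day − 1) / 30.44 months.

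| Group | Boosted | Not boosted | Ratio |
|---|---|---|---|
| A3 | 119 days, 3.9 months | 364 days, 12.0 months | 3.1 |
| A2 | 204 days, 6.7 months | 449 days, 14.8 months | 2.2 |

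A1 has no booster arm in Protocol Table 2. For healthy adults the booster day is 149 in Table 10 but 129 in Protocol 3.1.1, and these places must be reconciled. Rejection does not apply to that group.

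**3. Effect on the crude percentage, Part A stage.** Assumptions: constant hazard of 3% per year, everyone followed as planned, uptake f varied because it is not given. Risk over t days = 1 − exp(−0.03 × t / 365.25).

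- A3: 119 days gives 0.97%; 364 days gives 2.95%.
  - f = 50%: 0.5 × 0.97 + 0.5 × 2.95 = 1.96%, about 2.0%.
  - f = 90%: 0.9 × 0.97 + 0.1 × 2.95 = 1.17%, about 1.2%.
- A2: 204 days gives 1.66%; 449 days gives 3.62%.
  - f = 50%: 0.5 × 1.66 + 0.5 × 3.62 = 2.64%.
  - f = 90%: 0.9 × 1.66 + 0.1 × 3.62 = 1.86%.

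Over the full range of uptake, 0% to 100%, A3 runs from 2.95% down to 0.97% and A2 from 3.62% down to 1.66%. The hazard is the same throughout, so a person-time rate would stay at 3 per 100 person-years.

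**4. The same check in the combined Part A and Part B stage.** Boosted A3 participants have 119 + 180 = 299 days, against 364 unboosted. The risks are 2.43% and 2.95%.

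- f = 50%: 0.5 × 2.43 + 0.5 × 2.95 = 2.69%.
- f = 90%: 0.9 × 2.43 + 0.1 × 2.95 = 2.48%.

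The shift is about 0.2 percentage points, compared with about 0.8 in the Part A stage. For A2 the exposures are 204 + 180 = 384 and 449 days, again close. Columns that also include Group B4 still mix in participants with 180 days (5.9 months).

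**5. The 28-day stage.** It is a fixed window after each dose, so booster uptake does not change its length.

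**The case against.** The other side has several good points.

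- **The primary safety period is sound.** The 28-day stage is named as primary, and rejection is summarised in it too. A reader might infer that the main safety analysis is distorted; it is not.
- **One stage is not cut at the booster.** The combined stage matches the time frame of the primary endpoint and is nearly insensitive to uptake within a regimen. If it is read as covering only participants in both parts, planned follow-up within a regimen is uniform. The inference that all rejection reporting depends on uptake is therefore not supported.
- **Separate analysis is foreseen.** The SAP allows it, summarises study duration (6.2.6) and lists rejection cases individually (6.3.1.1). This helps a reader see the imbalance, but the split is optional and duration is never a denominator.
- **The contrast is easily overstated.** About 4 against about 15 months occurs in no single regimen, only in totals across regimens. The booster is due at least 4 months after the last dose. Enrolment was expected from April 2021, while Amendment 4 is dated 20 December 2021, so early enrolees may have longer Part A exposure than the nominal days imply.
- **No between-group comparison is planned.** True, but the study is meant for estimation, and an estimate that shifts with uptake is hard to interpret even within one group.
- **The shift is small against sampling error.** The size of A3 is not given. If it were 100, then 0.8 points is under one event, and exact 95% intervals for 1/100 and 2/100 are about 0.03% to 5.4% and 0.2% to 7.0%. This limits the practical effect for rejection, but does not give the percentage a time horizon.
- **Person-time is not a full cure.** It removes dependence on uptake only if the hazard is constant. If risk clusters after dosing, long unboosted follow-up dilutes the rate.

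**Conclusion.** The point holds for the Part A whole-study stage. There, the crude percentages for rejection, SAEs, MAAEs and AESIs combine planned exposures that differ 3.1-fold (A3) and 2.2-fold (A2) by booster status, with no exposure-adjusted figure and no mandatory split.

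Under a constant hazard of 3% per year and follow-up as planned, the A3 figure moves from 2.0% to 1.2% between 50% and 90% uptake. The hazard's time frame and the uptake are assumptions, so these sizes are illustrations. The dependence on uptake follows from the stage and denominator definitions, whatever the values.

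The point does not extend to the 28-day stage, and it barely touches the combined stage within a regimen. It is an inexpensive gap worth closing, since the SAP already uses person-time for infections. It does not show that the safety conclusions would be wrong.

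**What to change.** In SAP 6.3.1:

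1. Keep the crude percentages.
2. For adjudicated rejection, SAEs, MAAEs and AESIs in the whole-study stages, add the number of participants with a first event divided by person-time, with exact Poisson 95% confidence intervals.
3. End person-time where SAP 6.1 ends each stage: at the first event, the booster date (Part A stage only), study completion, discontinuation or death. Do not import the SAP 6.5.2 rule unchanged. It stops at the dose in the next part and at an efficacy cutoff, so it would wrongly censor the combined stage at the booster.
4. In SAP 6.1, make the split into boosted and unboosted participants mandatory for the Part A whole-study stage.
5. State that person-time corrects for length of follow-up only, not for self-selection into boosting or for a hazard that changes over time.

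Cost: SAP wording and a few extra table rows. The dates needed already feed the study-duration and infection summaries, so no new data are required.
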